4.4. Lifestyle Requirements

After confirmation of eligibility at Screen 3 (Visit 3) and starting at Run-in (Visit 4), subjects will be instructed to maintain the guidelines described below for the duration of participation in the study. These guidelines must be reiterated on Day 1 (Visit 6) and during site visits thereafter. The following guidelines are provided.

4.4.1. Meals and Dietary Restrictions

- Subjects must abstain from all food and drink (except water) for at least 8, but preferably 10 hours, prior to any blood sample collections for clinical laboratory tests.
 - Note: Subjects must abstain from all food and drink (except water) for ≥4 hours prior to ALL liver fat assessments, including Screen 1 and Screen 2.
- Blinded IPs should be administered twice daily with morning and evening meals and should be separated by at least 8 hours.
- Subjects will be instructed to maintain their normal diet throughout participation in the study (ie through Visit 11).

4.4.2. Alcohol, Caffeine, and Tobacco

• Intake of alcohol is permitted in moderation as defined in Section 4.2.

• Consumption of caffeinated drinks and nicotine-containing products is permitted during participation in the study; however, there may be a need for brief interruption while at the site and/or Imaging facility, depending on local policy.

4.4.3. Physical Activity

• Subjects will be asked to not engage in physically strenuous exercise (for example: heavy lifting, weight training, calisthenics, and aerobics) within 48 hours before blood sample collections for clinical laboratory tests.

4.4.4. Contraception

All fertile male subjects who are, in the opinion of the investigator, sexually active and at risk for pregnancy with their partner(s) must agree to use a highly effective method of contraception consistently and correctly for the duration of the active treatment period and for at least 28 days after the last dose of investigational product. The investigator or his or her designee, in consultation with the subject, will confirm that the subject has selected an appropriate method of contraception for the individual subject and his partner(s) from the permitted list of contraception methods (see below) and will confirm that the subject has been instructed in its consistent and correct use. At time points indicated in the Schedule of Activities, the investigator or designee will inform the subject of the need to use highly effective contraception consistently and correctly and document the conversation and the subject's affirmation in the subject's chart (subjects need to affirm their consistent and correct use of at least 1 of the selected methods of contraception). In addition, the investigator or designee will instruct the subject to call immediately if the selected contraception method is discontinued or if pregnancy is known or suspected in the subject or partner.

Highly effective methods of contraception are those that, alone or in combination, result in a failure rate of less than 1% per year when used consistently and correctly (ie, perfect use) and include the following:

- 1. Established use of hormonal methods of contraception associated with inhibition of ovulation (eg, oral, inserted, injected, implanted, transdermal), provided the subject or male subject's female partner plans to remain on the same treatment throughout the entire study and has been using that hormonal contraceptive for an adequate period of time to ensure effectiveness;
- 2. Correctly placed copper-containing intrauterine device (IUD);
- Male condom or female condom used WITH a separate spermicide product (ie, foam, gel, film, cream, or suppository). For countries where spermicide is not available or condom plus spermicide is not accepted as highly effective contraception, this option is not appropriate;
- 4. Male sterilization with absence of sperm in the post vasectomy ejaculate;

5. Bilateral tubal ligation/bilateral salpingectomy or bilateral tubal occlusive procedure (provided that occlusion has been confirmed in accordance with the device's label).

NOTE: Sexual abstinence, defined as completely and persistently refraining from all heterosexual intercourse (including during the entire period of risk associated with the study treatments) may obviate the need for contraception ONLY if this is the preferred and usual lifestyle of the subject.

All sexually active male subjects must agree to prevent potential transfer to and exposure of female partner(s) to drug through ejaculate by using a condom consistently and correctly, beginning with the dose of investigational product (Day 1) and continuing for at least 28 days after the dose of IP(s).

4.5. Sponsor's Qualified Medical Personnel

The contact information for the sponsor's appropriately qualified medical personnel for the study is documented in the study contact list located in the supporting study documentation.

To facilitate access to appropriately qualified medical personnel on study-related medical questions or problems, subjects are provided with a contact card. The contact card contains, at a minimum, protocol and investigational product identifiers, subject study numbers, contact information for the investigator site, and contact details for a contact center in the event that the investigator site staff cannot be reached to provide advice on a medical question or problem originating from another healthcare professional not involved in the subject's participation in the study. The contact number can also be used by investigator staff if they are seeking advice on medical questions or problems; however, it should be used only in the event that the established communication pathways between the investigator site and the study team are not available. It is therefore intended to augment, but not replace, the established communication pathways between the investigator site and the study team for advice on medical questions or problems that may arise during the study. The contact number is not intended for use by the subject directly, and if a subject calls that number, he or she will be directed back to the investigator site.

5. STUDY TREATMENTS

For the purposes of this study, and per International Conference on Harmonisation (ICH) guidelines, investigational product is defined as a pharmaceutical form of an active ingredient or placebo being tested or used as a reference/comparator in a clinical trial, including a product with a marketing authorization when used or assembled (formulated or packaged) in a way different from the approved form, or when used for an unapproved indication, or when used to gain further information about an approved use (ICH E6 1.33).

For this study, the investigational product(s) are PF-05221304 and PF-06865571 and their matching placebo. These will be administered as oral tablets.

5.1. Allocation to Treatment

Allocation of subjects to treatment groups will proceed through the use of an interactive response technology (IRT) system. The site personnel (study coordinator or specified designee) will be required to enter or select information including but not limited to the user's identification (ID) and password, the protocol number, and the subject number. The site personnel will then be provided with a randomization number and dispensable unit (DU) or container number. The IRT system will provide a confirmation report containing the subject number, randomization number, and DU or container number assigned. The confirmation report must be stored in the site's files. The study-specific IRT reference manual will provide the contact information and further details on the use of the IRT system.

Treatment Group	Treatment Regimen	Dosage ^a AM and PM		
А	Placebo (PF-05221304) BID Placebo (PF-06865571) BID	3 x Placebo (PF-05221304) tablets PLUS 3 x Placebo (PF-06865571) tablets		
В	15 mg PF-05221304 BID Placebo (PF-06865571) BID	3 x 5 mg PF-05221304 tablets PLUS 3 x Placebo (PF-06865571) tablets		
С	Placebo (PF-05221304) BID 300 mg PF-06865571 BID	3 x Placebo (PF-05221304) tablets PLUS 3 x 100 mg PF-06865571 tablets		
D	15 mg PF-05221304 BID 300 mg PF-06865571 BID	3 x 5 mg PF-05221304 tablets PLUS 3 x 100 mg PF-06865571 tablets		
a: Dosing in AM (with breakfast) and PM (with dinner) will be same				

 Table 6.
 Study Treatment Regimen and Dispensing Schedule

A computer generated randomization schedule will be used to assign approximately 98 subjects to one of the 4 treatment groups described in Table 6 in a randomization ratio of 1:2:2:2 for treatment groups A, B, C, and D respectively. The randomization number will be recorded in the case report form (CRF). The subject will receive the appropriate IP assigned by the IRT system.

In order to maintain the double-blind design:

- 5 mg PF-05221304 and matching placebo tablets will be the same size and shape; similarly, 100 mg PF-06865571 and matching placebo tablets will be the same size and shape.
- Each dose will consist of 6 white to off-white tablets representing PF-05221304/PF-06865571/placebo.
 - Note: For Visit 4 (Day -14) drug product dispensed will only consist of single-blind placebo to match PF-05221304 and PF-06865571 tablets.

5.2. Breaking the Blind

The study will be subject and investigator blinded.

At the initiation of the study, the investigator site will be instructed on the method for breaking the blind. The method will be an electronic process. Blinding codes should be broken only in exceptional circumstances when knowledge of the actual treatment code is absolutely essential for further management of the subject. Investigators are encouraged to discuss with a member of the study team if they believe that unblinding is necessary. When the blinding code is broken, the reason must be fully documented and entered on the case report form (CRF).

5.3. Subject Compliance

Compliance of single-blind placebo administration during the Run-in period will be assessed by pill count on Day 1 (Visit 6) for the purposes of inclusion into the study. Acceptable compliance will be defined as self-administration by the subjects of:

• $\geq 85\%$ of the study-supplied blinded placebo taken by the subject during the Run-In period (ie, Visit 4 to Visit 6) – up to 4 single doses are permitted to be missed.

Compliance of IP administration will be assessed during the treatment phase of the study by the number of tablets returned by the subjects at Visits 7, 8, 9 and 10.

• A compliance rate of ≥80% with self-administration of the IP is expected from Day 1 (Visit 6) to Day 42 (Visit 10); investigators must closely monitor non-compliant subjects in order to enhance their adherence to the study treatment. Subjects having missed more than 2-4 doses of IP during a one week treatment period will be re-educated on the importance of compliance on their site visit. If similar non-compliance is noted on their next site visit also, the subject may be discontinued from the study, upon discussion with the Sponsor.

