A fixed, single-blind placebo run-in period of approximately 14 days (from Visit 4 to Visit 6) following confirmation of eligibility and prior to randomization is included to familiarize subjects with the study treatment regimen and to exclude subjects who are not compliant with single-blinded placebo administration prior to randomization at Visit 6. To date, clinical experience with PF-05221304 and PF-06865571 co-administration is limited to a PK drug-drug interaction (DDI) study (C3711002) with a total of 1 week duration of combined drug exposure in an inpatient setting. In this study, with longer and predominantly outpatient dosing in a patient population, close safety monitoring will be implemented with frequent (every 2 weeks) outpatient visits post randomization, including an additional, early visit at Day 5 (Visit 7).

Total duration of PF-05221304 and PF-06865571 co-administration in this study will be approximately 6 weeks, supported by a completed 6-week non-clinical combination toxicity study in monkeys. This duration is expected to allow assessment of effects of co-administration of PF-05221304 and PF-06865571 on liver fat content, as well as on safety and tolerability of these agents.

In this study PF-05221304 and PF-06865571 co-administration will be required to occur twice daily with food (breakfast and dinner).

This study is designed to assess the effect of PF-05221304 and PF-06865571 on liver fat and other PD biomarkers that are intended to provide insight into metabolic pathways related to ACC and DGAT2 inhibition. Specifically, the study will evaluate the effect of PF-05221304 and PF-06865571 combination on liver fat and liver function [ie, alanine aminotransferase (ALT), aspartate aminotransferase (AST), alkaline phosphatase and gamma-glutamyl transferase (GGT)], glycemic parameters, and fasting lipids including total cholesterol, low-density lipoprotein cholesterol (LDL-C), high-density lipoprotein cholesterol (HDL-C) and triglycerides (TGs). In addition, effect on other PD parameters [ie apolipoproteins A1, B (total), C3, CCI

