6.2. Run-in Period (Visit 4)

After the investigator has determined all eligibility criteria have been satisfied (approximately within 1 week following Visit 3), subjects will return to the site after a minimum 8-hour, but preferably 10-hour fast (except water). The single-blind Run-in period will serve to familiarize the subject with the study treatment regimen and exclude subjects who are not compliant with dosing. This visit will occur 14±2 days prior to the planned date of randomization (Visit 6, Day 1).

For all subjects, refer to the Schedule of Activities for the study procedures to be completed at the Run-in visit (Visit 4).

Following completion of the above procedures, single-blind IP will be self-administered (with meal) while witnessed by adequately trained site staff. Subjects will then be discharged from the site with enough IP to last until Day 1 (Visit 6).

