6.4. Study Period

6.4.1. Day 1 (Visit 6)

Approximately 14 days after Visit 4, subjects will return to the site after a minimum of an 8-hour, but preferably 10-hour fast.

Subjects will be asked to return IP dispensed at Visit 4 for an assessment of the pill count. Subjects must be at least 85% compliant with the placebo run-in IP in order to be randomized.

Refer to the Schedule of Activities for the study procedures to be completed prior to administration of IP on Day 1. Be sure to collect a genomic banked biospecimen for OATP genotyping. If missed, collect at the next available time point when biospecimen are being collected in conjunction with a subject visit.

Subjects who meet safety eligibility ie, ECG, vitals and weight, liver fat eligibility as determined by FibroScan (CAPTM ≥280 dB/m) and MRI-PDFF (≥8%), compliance criteria (>85% compliant) and are negative for urine drug test will be randomized to double-blind study treatment on Day 1. Sites will contact the IRT system for assignment of double-blind treatment. Double-blind IP(s) will be dispensed to subjects via IRT and self-administered. Following witnessed dosing of IP (with meal), an approximate 2-week supply of double-blind IP will be dispensed, and subjects will be discharged from the site.

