6.4.2. Day 5 (Visit 7)

At 5 ± 1 days from Visit 6, subjects will return to the study site after a minimum of an 8-hour, but preferably 10-hour fast. Subjects will bring un-used supply of IP for compliance check.

• Note: If subjects do not meet at least 80% compliance, subjects will be re-educated on the importance of dosing compliance.

Refer to the Schedule of Activities for the study procedures to be completed prior to administration of IP on Day 5.

Following witnessed dosing of IP (with meal), subjects will be discharged from the site with their un-used IP, to be taken for remainder of the days until their next visit (Visit 8).

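### Section 5.3's allowance of four missed run-in doses falls below the 85% randomisation cut-off for the 12- and 13-day run-ins that Section 6.2 permits (minor)

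*Protocol*

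**What the plan says.** **Run-in.** Protocol Section 5.3 defines acceptable run-in compliance, by pill count at Visit 6, as 85% or more of the single-blind placebo, and glosses this with "up to 4 single doses are permitted to be missed". Section 6.4.1 makes the percentage a condition of entry: "Subjects must be at least 85% compliant with the placebo run-in IP in order to be randomized". It gives no dose count. Section 1.6.1 describes the run-in as lasting about 14 days, but Section 6.2 and the Schedule of Activities give Visit 4 a window: "This visit will occur 14±2 days prior to the planned date of randomization". Footnote k of the Schedule sets dosing at twice daily in both the single-blind and double-blind periods.

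**On treatment.** Section 5.3 expects 80% compliance and states the action rule as a weekly count: "Subjects having missed more than 2-4 doses of IP during a one week treatment period will be re-educated on the importance of compliance". The stated measure is a pill count at Visits 7 to 10: "Compliance of IP administration will be assessed during the treatment phase of the study by the number of tablets returned by the subjects". Section 6.4.2 states the Day 5 rule as a percentage: "If subjects do not meet at least 80% compliance, subjects will be re-educated on the importance of dosing compliance". Section 6.4.3 uses the same 80% at Days 14 and 28.

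**The concern.** A percentage cut-off and a fixed dose count agree only for certain numbers of scheduled doses. The run-in length may vary by two days either way, so the number of scheduled doses varies too, yet Section 5.3 gives one count for all lengths. If the count is too generous at the short end, a site that works from it could randomise a subject whom Section 6.4.1 says must not be randomised. The run-in exists partly to exclude subjects who do not take the study medication, so this is a wrong figure attached to an eligibility test.

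The on-treatment wording raises a lesser question. A trigger expressed as a range, 2-4, does not tell a site at which missed dose to act.

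**Working it through.** **Inputs**
- Cut-off: 85% (Sections 5.3 and 6.4.1).
- Stated allowance: 4 missed doses (Section 5.3).
- Run-in length: 14±2, so 12 to 16 days (Section 6.2, Schedule of Activities).
- Frequency: 2 doses a day (Schedule, footnote k).
- Tablets per dose: 6 (Section 5.1).

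**Formulas.** Run-in doses run from the morning of Visit 4 to the evening before Visit 6, so N = 2 × days. Compliance with m missed = (N − m)/N. The largest m that still meets 85% is 0.15 × N rounded down.

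**The plan's own figure.** At 14 days N = 28. Four missed gives 24/28 = 85.7%; five missed gives 23/28 = 82.1%. Four is correct at the nominal length.

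**All permitted lengths**

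| Run-in (days) | N | 4 missed | Meets 85%? | 0.15 × N | Most that may be missed |
|---|---|---|---|---|---|
| 12 | 24 | 20/24 = 83.3% | No | 3.6 | 3 |
| 13 | 26 | 22/26 = 84.6% | No | 3.9 | 3 |
| 14 | 28 | 24/28 = 85.7% | Yes | 4.2 | 4 |
| 15 | 30 | 26/30 = 86.7% | Yes | 4.5 | 4 |
| 16 | 32 | 28/32 = 87.5% | Yes | 4.8 | 4 |

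The shortfall is 85 − 83.3 = 1.7 percentage points at 12 days and 85 − 84.6 = 0.4 at 13 days.

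**Does another way of counting rescue the figure?**
- *Leave out the witnessed Visit 4 dose:* 19/23 = 82.6% and 21/25 = 84.0%. Both still fail.
- *Add the Visit 6 morning dose:* 21/25 = 84.0% and 23/27 = 85.2%. The 13-day case would pass, but that dose is double-blind product, not run-in placebo, and 12 days still fails.
- *Divide by the full 16-day supply (32 doses, Section 5.4.1):* perfect adherence over 12 days would score 24/32 = 75%, so this cannot be the intended denominator.
- *Count tablets:* four doses are 24 tablets. The 85% rule allows 21 missed of 144 at 12 days and 23 of 156 at 13 days. Both still fail.

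Section 6.4.1 also states the cut-off once as strictly above 85%. In whole doses this makes no difference, because none of 24, 26, 28, 30 or 32 doses can give exactly 85%.

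**Weekly re-education trigger.** One week is 14 doses. With 2, 3, 4 and 5 missed, compliance is 85.7%, 78.6%, 71.4% and 64.3%. Depending on whether the range is read as more than 2, 3 or 4, action first falls at 3, 4 or 5 missed. Only more than 2 matches the 80% rule over a week. The scheduled gaps between the counts at Visits 7, 8, 9 and 10 are 9, 14 and 14 days, so those counts do not normally yield a one-week figure.

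**The case against.** The strongest reply is that the percentage governs. Section 5.3 states 85% first, the count is an appended illustration for the planned run-in of about 14 days, where it is exact, and the instruction applied at Visit 6 in Section 6.4.1 uses only the percentage. Harm needs a site to use the count and overlook both statements of the percentage. This stands as a reason to rate the point minor and to correct the count rather than the percentage. It does not make the count right: a 12-day run-in is within window and is not a deviation, and the text ties the allowance to no particular length.

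A second reply reads the four doses as a cap applied alongside 85%, so that a short run-in with four misses fails anyway. The wording says that those misses are permitted, which is more than a ceiling.

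Three stronger readings are tempting but not supported:
- *The on-treatment rules contradict each other.* They do not. Sections 6.4.2 and 6.4.3 give a working 80% rule, and a site can satisfy both by acting on either trigger. The weekly clause is imprecise, and it matters only for counselling.
- *The repeat-failure rules conflict.* Section 5.3 speaks of the next site visit and Section 6.4.3 of a second occurrence. Both are permissive and involve the Sponsor, and nothing in Section 5.3 forbids acting under Section 6.4.3.
- *The treatment comparison is biased.* The run-in check precedes randomisation, and SAP Section 4.2 uses no per-protocol set, so no analysis set is defined by adherence.

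**Conclusion.** The point holds and is minor. The four-dose allowance contradicts the 85% randomisation cut-off at 2 of the 5 permitted run-in lengths, and only for a subject who misses exactly four doses: with three missed, compliance is at least 87.5% at every length, and five missed exceeds the allowance. The number of subjects affected cannot be estimated, because the documents give neither the share of 12- and 13-day run-ins nor a rate of missed doses.

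The result assumes two scheduled doses on each run-in day, with the double-blind dose at Visit 6 not counted as run-in placebo. Sample size, power and the primary analysis are unaffected. The weekly trigger is a matter of tidying, not an error of the same kind.

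**What to change.** In Section 5.3, delete the four-dose gloss and keep 85% or more of scheduled run-in doses as the only cut-off. If a count is wanted for sites, state it by length: at most 3 missed for 12 or 13 days, at most 4 for 14 to 16 days.

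As optional tidying in the same edit, replace the weekly 2-4 dose trigger with the rule of Sections 6.4.2 and 6.4.3: below 80% of the doses scheduled since the previous pill count. Two details matter:
- *Let the percentage govern, with no fixed dose count.* A count would repeat the run-in fault. Five missed is 23/28 = 82.1% over the nominal 14 days from Visit 8 to Visit 9, but 15/20 = 75.0% over the 10 days that the windows allow.
- *Measure from the previous count, not the last dispensing.* Nothing is dispensed at Visit 7. A subject who missed six doses before Visit 7 and none after it would still score 20/26 = 76.9% at Visit 8 if measured from Visit 6, so the same misses would count twice.

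The change is wording in Section 5.3 only, with no new visit, procedure, supply or sample size. An amendment needs prospective ethics approval (Section 12.1) across about 30 sites, so this can be bundled with the next one.
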